8.0 Study Calendar

Parent Pilot Test Data Collection Schedule	
Baseline (T1)	
 • Demographics/Health Literacy (8 questions) • Decisional Conflict Scale (DCS) (16 questions) • Decision-Specific Knowledge Test (6 questions) • Treatment Preference/Awareness of Decision (2 questions) 
Recommendation: Have any of your child’s healthcare providers already made a recommendation about your son’s hypospadias? If so, what was the recommendation? (1 question)

Pre-consultation, 1 week after baseline (T2)	
 • Website Viewed (3 questions) 
 ○ Did you have time to look at the website ○ Did you view the website with anyone else? ○ Did you view the website on a smart phone, tablet, or computer? • Treatment Preference/Awareness of Decision (2 questions) • Decisional Conflict Scale (DCS) (16 questions) • Decision-Specific Knowledge (6 questions)

	
 • Decision Aid Acceptability Questionnaire (4 questions) • Preparation for Decision Making Scale (10 questions)
Initial post-consultation, within 48 hours of urology visit (T3)	
 • Treatment Preference/Awareness of Decision (2 questions) • Decisional Conflict Scale (DCS) (16 questions) • Shared Decision Making Questionnaire (SDM-Q-9) (9 questions) • Preparation for Decision Making Scale (PrepDM) (10 questions) • Open-ended questions (3 questions) 
 ○ What most impacted your decision during/after your visit with the urologist? ○ How did you use the decision aid during your visit with the urologist? ○ Is there anything we didn't cover that you would like to share?
3-month post-consultation (T4)	
 • Decision Regret Scale (5 questions) • Open-ended questions (2 questions) 
 ○ What do you wish you would've known when you were making the decision? ○ Is there anything that we didn't cover that you would like to share?

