17.0 Appendix

To assess the quality of the decision-making process and the impact of the decision aid, we will utilize these scales:

- **Decisional Conflict Scale (DCS).** DCS is a validated scale that has been extensively studied and consists of 10 statements and 5 response categories ranging between 0 (no decisional conflict) and 100 (extremely high decisional conflict).
- **Decision-Specific Knowledge.** We used data from Aims 1 and 2 to inform the development of a questionnaire to determine decision-specific knowledge of hypospadias treatment options/outcomes. We decided a priori that a score of 80% must be attained on this questionnaire as an indicator of being “informed.”
- **Hypospadias Treatment Preference/Awareness of Decision.** Parents will be asked whether they intend to have their child undergo hypospadias surgical repair and whether they are aware that there is a decision to be made.
- **Decision Aid Acceptability Questionnaire.** We will also assess the acceptability of the DA using a tool similar to the Decision Aid Acceptability Questionnaire. Questions will elicit feedback on amount of content, clarity, and helpfulness of the DA, acceptability of format and whether the information was presented in a balanced and fair manner.
- **Preparation for Decision Making Scale (PrepDM).** This 10-item scale assesses a patient's perception of how useful a decision aid is in preparing the respondent to communicate with their practitioner at a consultation focused on making a health decision.
- **Shared Decision Making Questionnaire (SDM-Q-9):** This is a 9-item self-report instrument developed to measure the process of SDM as perceived by the patient. The scale has high internal consistency, high item discriminations, and showed high face and factorial validity.
- **Decision Regret Scale:** The Decision Regret Scale measures distress or remorse after a health care decision. We will perform an early assessment of DR in this study with plans to re-assess the long-term level of regret in a future randomized controlled trial.

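### Decision regret is scored only at T4 with no record of decision or surgery status, so the score may pool parents in different positions

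*Combined protocol and SAP*

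**What the plan says.** Section 3.0 (Pilot Testing Objectives) lists decisional regret among seven secondary outcomes. The primary outcomes are feasibility and acceptability.

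Section 8.0 (Study Calendar) places regret at one time point, "3-month post-consultation (T4". The entry is "Decision Regret Scale (5 questions", followed by two open-ended questions. The first of these asks what parents wish they had known "when you were making the decision", so it takes a decision for granted.

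The calendar's only structured item on choice is "Treatment Preference/Awareness of Decision (2 questions". It appears at T1, T2 and T3. The T3 call is headed "Initial post-consultation, within 48 hours of urology visit (T3". According to section 17.0 (Appendix), the item asks "whether they intend to have their child undergo hypospadias surgical repair" and whether they know that there is a decision to make.

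The same appendix defines the regret construct: "The Decision Regret Scale measures distress or remorse after a health care decision". It calls the T4 measurement an early one and plans to look at long-term regret in a later randomised trial. Section 12.0 (Statistical Considerations) promises descriptive statistics for all quantitative data, wants variance and correlation estimates for a larger study, and plans no sub-analyses.

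**The concern.** A regret score presupposes a decision to regret. T4 is timed from the consultation, not from a decision or an operation, and nothing asked at that call establishes where the parent stands. A parent who is still undecided, one waiting for an operation date, one whose son has had surgery and one who turned surgery down would all answer the same five items. Each would be answering about something different: no settled choice, a choice not yet acted on, a choice whose result is already visible, or a choice not to operate.

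Such a mix is plausible in this population. Section 4.1 prefers parents who have not settled on surgery at enrolment, and section 1.0 describes delay and wavering as signs of the decisional conflict under study.

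What is at stake is the meaning of one secondary outcome, and of the regret mean and variance that a larger trial would take from this pilot.

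**Working it through.** The plan states no figure for regret (no SD, threshold or test), so there is nothing to reproduce. The check is of what is collected and what could be recovered from it.

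**Step 1. Calendar check (section 8.0).**

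| Time point | Intention/awareness item | Decision-made item | Surgery-status item | Regret scale |
|---|---|---|---|---|
| T1 | yes | no | no | no |
| T2 | yes | no | no | no |
| T3 | yes | no | no | no |
| T4 | no | no | no | yes |

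A decision-made item appears at 0 of 4 time points, and so does a surgery-status item. Intention and regret are never recorded at the same call, and about three months separate the last intention record from the regret score.

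**Step 2. Could status be recovered from elsewhere?**

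- *T3 intention.* It allows a rough split by intended choice. It cannot show a later change of mind, a decision still open at T4, or whether surgery has taken place.
- *Open-ended answers at T3 and T4.* Status may come up, but no question asks for it. Section 12.0 treats qualitative results as tertiary or exploratory.
- *Other sources.* The documents describe no chart review or other record of surgery.

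**Step 3. Do the withdrawal rules settle it?**

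| Position at T4 | Section 4.2 (urologist finds no hypospadias: withdrawn) | Section 11.0 (urologist recommends no surgery: withdrawal allowed, not required) |
|---|---|---|
| Undecided about an offered operation | not removed | not removed |
| Waiting for surgery | not removed | not removed |
| Surgery done | not removed | not removed |
| Declined an offered operation | not removed | not removed |

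Both rules turn on the urologist's finding or advice. Neither turns on what the parent decided.

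**Step 4. Consequence for the summary statistics.** Let status group k have share p_k, mean regret m_k and variance v_k. For the pooled T4 sample:

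- mean m = Σ p_k m_k
- variance = Σ p_k v_k + Σ p_k (m_k − m)²

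If the group means differ, the second variance term is positive. The pooled mean and variance then depend on the shares p_k, which this plan does not record. If all respondents share one status, or the group means are equal, that term is zero. The plan gives no structured means of telling which case applies.

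**Step 5. Size.** The documents give no share for any status. With n completers, the number without a decision could be anything from 0 to n. Section 7.1 plans 10 to 25 completers with a ceiling of 40. Four status groups (undecided, done, scheduled, declined) would average 10/4 = 2.5, 25/4 = 6.25 and 40/4 = 10 parents each.

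**Step 6. Room at T4.** Using the calendar's own item counts:

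- T1 = 8 + 16 + 6 + 2 + 1 = 33
- T2 = 3 + 2 + 16 + 6 + 4 + 10 = 41
- T3 = 2 + 16 + 9 + 10 + 3 = 40
- T4 = 5 + 2 = 7

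Section 7.1 allows 10 to 30 minutes for every call. One more item takes T4 from 7 to 8.

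**The case against.** The best defence is that the stakes are low and the group is less open than it looks. Regret is one of seven secondary outcomes in a pilot. It is measured once, so the planned pre/post comparison does not apply to it, and no test or threshold is attached. Parents whose son proves not to have hypospadias leave the study, and those advised against surgery may leave. T3 intention is recorded after the consultation, and the interviews may be recorded and transcribed, so in a sample this small an analyst could piece together some of the picture. All of this stands, and it limits the point to interpretation of one secondary outcome. It does not supply the missing status.

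Three stronger readings are tempting, and the documents do not support them:

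- *That the T4 score does mix these groups.* Neither the status mix at three months nor the time to surgery is given. Mixing is something that the plan permits and could detect only roughly.
- *That an undecided parent has no defined regret score.* The appendix gives the construct but not the items, the scoring or the handling of undecided respondents. Such a score is hard to interpret; the documents do not show that it is undefined.
- *That the groups could never be separated afterwards.* T3 intention and incidental remarks would allow a rough split.

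It could also be said that section 12.0 plans no sub-analyses. Describing who contributed to a score is not an inferential subgroup analysis, so that statement does not conflict with the change.

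**Conclusion.** The point holds as an inexpensive improvement to a secondary outcome. If the plan is followed exactly, it yields a regret mean and variance from parents whose decision and surgery status is unrecorded at the time of scoring, on a scale that the appendix ties to a decision already made. The withdrawal rules and T3 intention reduce the ambiguity without resolving it.

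No numerical size can be given, because the share of parents in each position is not in the documents and any assumed share would be a guess. The conclusion does not depend on one. It rests on the calendar being complete as listed and on there being no other source of surgery status, since none is described. The feasibility and acceptability conclusions do not depend on regret and are untouched.

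**What to change.** Add one structured item to the T4 call: has a decision been made, or is the parent undecided; and, if made, is surgery done, scheduled or declined. State in section 12.0 that regret is reported for all T4 respondents and also shown descriptively by status, with parents who report no decision identified separately. The mean and variance taken to the larger trial can then be read with the composition in view.

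Restricting the score to parents who report a decision is not recommended as the main summary. Decision status arises after the decision aid has been used and may be affected by it, so the restriction would select on a post-intervention variable and shrink a small sample.

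The cost is about a minute per parent and a minor amendment. The status table will have small cells and should carry no tests.

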9.0 Reportable Events

We will assess for adverse events (AE) and actively monitor for a security breach or protocol deviations that might affect the confidentiality or privacy of the sensitive data we store, manage and analyze. If there are any AEs identified, we will report these to the Institutional Review Board (IRB) within the required timeframe.

10.0 Data Safety Monitoring

There will be regular review meetings that will occur, at a minimum, quarterly throughout the year. The study team will review current accrual, data management concerns, and data analysis/interpretation.

11.0 Study Withdrawal/Discontinuation

If a parent or provider wishes to withdraw from the study, s/he may inform the research assistant or PI at any point and s/he will be withdrawn from the study immediately. If the consented parent did not attend the urology visit or if the study team is unable to reach the parent or unable to collect Timepoint 2 before the urology visit occurs, then the parent will be withdrawn. Additionally, if the urologists recommends no surgery, in typically mild cases, then the parent may be withdrawn. Parents may be notified of withdrawal by email, text, or phone call.

12.0 Statistical Considerations

To inform sample size calculations and feasibility for a larger trial, we will analyze data as in a larger study and generate estimates of variance and correlation.⁹ We will check all quantitative data for departures from normality and analyze it with descriptive statistics. We will compute measures of central tendency and dispersion for continuous variables, and frequencies and proportions for categorical variables.

To examine the effect of the DA on decisional conflict and knowledge, we will examine differences between pre- and post-intervention measures (i.e. the decisional conflict scale and the decision-specific knowledge test) using paired t-tests or Wilcoxon signed-rank tests for all continuous measures.

As this protocol focuses on appropriateness, acceptability and pilot testing of the DA, no sub-analyses are planned. We will plan to undertake examination of the influence of participant characteristics in future studies.

We will analyze all transcribed qualitative data, including parent participant and provider follow-up interviews, using inductive thematic qualitative content analysis.^{7,8} The frequency, extensiveness, and specificity of comments will guide data categorization into recurrent themes.^{7,8} We will alter and refine these themes through a recursive process from the data to analyst-generated categorical and conceptual definitions. The qualitative results are considered to be tertiary/exploratory as the findings provide additional context to the quantitative scores. The qualitative results are not primary or secondary outcomes of this study.

13.0 Statistical Data Management

Primary data for surveys and interviews will be collected, managed, and stored electronically in REDCap and/or the secure department server. During data collection, any questions or concerns will be flagged in the REDCap database for PI review. Additional quality assurance steps will include: testing of database by study team prior to moving to production mode and extraction and cleaning of data that will be used for analysis every two months.

14.0 Privacy/Confidentiality Issues

This study presents a minimal risk of loss of confidentiality. Efforts will be made to keep personal information confidential. We cannot guarantee absolute confidentiality. Personal information may be disclosed if required by law. Participant identity will be held in confidence in reports in which the study may be published and databases in which results may be stored. Participants will have the option to pass/skip any questions or activities that they do not want to answer or participate in. Any study data used for dissemination, publications, or the decision aid will be de-identified with the exception of the parent testimonial videos.

15.0 Follow-up and Record Retention

The study will continue through December 2023. After that, records will be retained for the minimum time allowed by law and then de-identified or destroyed.

17.0 Appendix

To assess the quality of the decision-making process and the impact of the decision aid, we will utilize these scales:

- **Decisional Conflict Scale (DCS).** DCS is a validated scale that has been extensively studied and consists of 10 statements and 5 response categories ranging between 0 (no decisional conflict) and 100 (extremely high decisional conflict).
- **Decision-Specific Knowledge.** We used data from Aims 1 and 2 to inform the development of a questionnaire to determine decision-specific knowledge of hypospadias treatment options/outcomes. We decided a priori that a score of 80% must be attained on this questionnaire as an indicator of being “informed.”
- **Hypospadias Treatment Preference/Awareness of Decision.** Parents will be asked whether they intend to have their child undergo hypospadias surgical repair and whether they are aware that there is a decision to be made.
- **Decision Aid Acceptability Questionnaire.** We will also assess the acceptability of the DA using a tool similar to the Decision Aid Acceptability Questionnaire. Questions will elicit feedback on amount of content, clarity, and helpfulness of the DA, acceptability of format and whether the information was presented in a balanced and fair manner.
- **Preparation for Decision Making Scale (PrepDM).** This 10-item scale assesses a patient's perception of how useful a decision aid is in preparing the respondent to communicate with their practitioner at a consultation focused on making a health decision.
- **Shared Decision Making Questionnaire (SDM-Q-9):** This is a 9-item self-report instrument developed to measure the process of SDM as perceived by the patient. The scale has high internal consistency, high item discriminations, and showed high face and factorial validity.
- **Decision Regret Scale:** The Decision Regret Scale measures distress or remorse after a health care decision. We will perform an early assessment of DR in this study with plans to re-assess the long-term level of regret in a future randomized controlled trial.

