7.0 Study Procedures

7.1 Parent Pilot Testing of Decision Aid

Research assistants will collect data from parents at four time points, twice before and twice after their son's first visit with a pediatric urologist/pediatric urology nurse practitioner for a potential or actual diagnosis of hypospadias. The questions will address website usability,

feedback on content, usefulness in decision-making, and basic demographic questions. Data will be collected via phone interview with a research assistant. Interviews may be recorded and professionally transcribed for analysis. Reminders will be sent to parents between the four time points regarding looking at the website and the upcoming data collection calls. We anticipate that each data collection point will require 10-30 minutes for parents to complete. We will also use a website plug-in to track any analyze how parents move through the website. We plan to interview 10-25, but no more than 40 parents (n=40) who complete all timepoints of the study.

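### Does the mismatch between 16 and 10 items for the Decisional Conflict Scale require a change to the plan?

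*Combined protocol and SAP*

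**What the plan says.** The data collection schedule in Section 8.0 lists "Decisional Conflict Scale (DCS) (16 questions") at baseline (T1), before the consultation (T2) and within 48 hours after it (T3). The DCS is not scheduled at T4.

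Section 17.0 opens with "To assess the quality of the decision-making process and the impact of the decision aid, we will utilize these scales", and its DCS entry says the scale "consists of 10 statements and 5 response categories ranging between 0 (no decisional conflict) and 100 (extremely high decisional conflict").

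Section 3.0 places decisional conflict among the secondary outcomes. Section 12.0 names the DCS and the knowledge test as the measures to be compared before and after the decision aid, by paired t-test or signed-rank test. It also gives a planning purpose: "To inform sample size calculations and feasibility for a larger trial", the team writes, "we will analyze data as in a larger study and generate estimates of variance and correlation". Neither Section 3.0 nor Section 12.0 states an item count.

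**The concern.** The Appendix presents its list as the instruments this study will use, so its DCS entry cannot be set aside as general background. A reader of both sections cannot tell for certain which form produced the score. The DCS is one of only two measures named for judging the effect of the decision aid, and lower decisional conflict is the study's central hypothesis. The pilot is also meant to supply variance and correlation estimates for a larger trial, and such estimates belong to a particular version of a scale. If the fielded form had 16 items and a planner took the Appendix's 10-item description as the form behind the variance, the later sample size could be somewhat off.

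**Working it through.** **1. The counts side by side.** Three scales have an item count in both sections.

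| Scale | Section 8.0 | Section 17.0 |
|---|---|---|
| DCS | 16 (T1), 16 (T2), 16 (T3) | 10 |
| PrepDM | 10 | 10 |
| SDM-Q-9 | 9 | 9 |

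Only the DCS disagrees, by 16 − 10 = 6 items. The calendar repeats its figure three times, including "Decisional Conflict Scale (DCS) (16 questions) • Decision-Specific Knowledge Test (6 questions") at T1 and "Decisional Conflict Scale (DCS) (16 questions) • Decision-Specific Knowledge (6 questions") at T2, and the Appendix sentence is intact, so this is not a fault of text extraction. No section mentions a short form, a subset of items or an alternative version. The calendar is the collection schedule and agrees with itself, so 16 is the likelier count, but the document does not prove it.

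**2. Does the 0–100 range settle it?** Assume that the five categories are coded 0 to 4 (the document does not give the coding). Sixteen items give a raw total of 0 to 64, and one raw point is 100/64 = 1.5625 scale points. Ten items give 0 to 40, and one raw point is 100/40 = 2.5. Both rescale to 0–100, so the range fits either form.

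**3. Could the slip corrupt the scoring?** The database holds one field per item asked, so the analyst sees how many there are. Using a 10-item divisor on 16 items would give a maximum of 64/40 × 100 = 160, outside the stated range.

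**4. What depends on the count?**
- Paired comparison: the same count is scheduled at T1, T2 and T3, so differences are taken on one form, whichever it is.
- Primary outcomes: screening, enrolment, retention and acceptability do not use the DCS.
- Thresholds: the 80% criterion for being informed applies to the knowledge test.
- Sample size: the document has no power calculation.

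**5. The carry-over to a later trial, as an illustration only.** Suppose a planner used a 16-item variance for a 10-item form. Assume that the score is a simple item mean, that all items have equal variance and a common correlation r, and that the 10 items behave like any 10 of the 16. None of this is in the document. Then Var(mean of k items) = s²(1 + (k − 1)r)/k, so V10/V16 = 1.6(1 + 9r)/(1 + 15r). With sample size proportional to variance, the shortfall is 1 − V16/V10.

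| r | V10/V16 | Shortfall |
|---|---|---|
| 0.1 | 3.04/2.5 = 1.216 | 17.8% |
| 0.3 | 5.92/5.5 = 1.076 | 7.1% |
| 0.5 | 8.8/8.5 = 1.035 | 3.4% |
| 0.7 | 11.68/11.5 = 1.016 | 1.5% |

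The result depends heavily on r: at r = 0 the ratio is 1.6. If the later trial uses the form fielded in the pilot, the ratio is 1 and there is no shortfall.

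**The case for a change.** The strongest case for a correction is that the contradiction is plain, concerns one of the two measures used to judge the decision aid, and costs one line to remove. The innocent readings fail: the text is not garbled, the Appendix is describing this study's instruments, and the other scales' counts agree. The pilot's variance estimates are also of little use to others unless the version is known.

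Most of this stands as description. The mismatch exists, and a report of DCS results should name the version used. What does not stand is the step from there to a change in the plan. Correcting the count would alter no data collected, no test and no estimate. The planning harm needs someone designing a later trial to overlook the form that the pilot actually used, when the item-level data show it. The percentages in the illustration describe that assumed mistake on assumed correlations; they do not measure a defect in this plan.

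**Conclusion.** The inconsistency is real and clerical: 16 items in the calendar, at three time points, against 10 in the Appendix. Its effect on this study's primary outcomes, paired comparison and stated numbers is nil, provided that one form is used at every visit, as the calendar shows. The possible carry-over to a larger trial has no fixed size. It is zero if the same form is used there, and otherwise about 1.5% to 18% of the required sample size for inter-item correlations from 0.7 down to 0.1, under the assumptions given. Analysts will score the items that were asked and can name the version when they report. No change to the plan is called for.
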